## **10. CHANGES FROM THE PLANNED ANALYSES**

The following changes to study protocol V3.0 (dated 06May2019) are implemented in this SAP:

- As requested by US FDA, inference for the primary and secondary efficacy endpoints will be evaluated using a one-sided test at the 0.025% significance level.
- The primary and secondary efficacy analyses will be performed including all subjects. Subjects with baseline dystrophin levels [REDACTED] predicted will not be removed from the primary and secondary efficacy analyses.
- Sensitivity analyses excluding subjects with baseline dystrophin levels [REDACTED] predicted will be added to both primary and secondary efficacy endpoints.

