## 8 STATISTICAL CONSIDERATIONS

### 8.1 Statistical Hypotheses

The null hypothesis of this study is that the change in dystrophin levels following 40 weeks of ataluren therapy, as measured by an immunoassay such as ECL is zero with the alternative hypothesis being that the change is greater than zero. To evaluate this hypothesis a one-sided test at the 5% alpha level will be employed.

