### 3.3. Sample Size Determination

Approximately, 15 to 20 ataluren-naïve male subjects, aged  $\geq 2$  and  $< 8$  years of age is planned to be enrolled in this study. Limited information is available about the magnitude and intra-subject variability of the change in dystrophin levels, as measured by an immunoassay such as ECL following 40 weeks ataluren therapy in this patient population. Assuming a baseline dystrophin level of 0.2% of control levels (as per previous dystrophin replacement therapy [Center for Drug Evaluation and research Application number: 206488Orig1s000 Eteplirsen Summary Review]), Table 1 shows the number of subjects needed to achieve an 85% power to detect an increase from baseline in dystrophin of 0.04%, 0.06% and 0.08%, for intra-subject coefficients of variability ranging from 20% to 35%, using a one-sided test at alpha 5%. As an example, if the increase from baseline is 0.08% and the intra-subject coefficient is 30%, 13 evaluable subjects would be required to have a power of 85% to detect this increase.

**Table 1: Summary of number of subjects required to achieve 85% power to detect increase in dystrophin levels from baseline**

Increase of dystrophin from baseline	Intra Subject CV			
	20%	25%	30%	35%
0.04%	19	29	41	55
0.06%	10	15	21	28
0.08%	7	10	13	18

**Abbreviations:** CV, coefficients of variability

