### 5. GENERAL CONSIDERATIONS

#### 5.1. Tables, Figures, and Listings

In general, continuous variables will be summarized using descriptive statistics including n (number of subjects), mean, standard deviation, median, minimum, and maximum. Categorical variables will be summarized using frequency count as number and percentage of subjects. Unless specified, all hypothesis testings are 1-sided at a 5% alpha level.

By subject data listings will be created for selected electronic case report form (CRF) domains sorted by subject and associated dates.

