#### **5.5. Multicenter, Multiplicity control**

This is a multicenter study with all muscle biopsies performed at one center. No multicenter analysis will be conducted for this study.

There is only one primary efficacy endpoint, and one secondary efficacy endpoint for this study. The secondary efficacy endpoint will be analyzed if the primary efficacy endpoint is statistically significant at 0.05 significance level. All other endpoints and analyses are supportive. Therefore, no multiplicity adjustment will be conducted for this study.

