### 7.1. Primary Efficacy Analyses

#### 7.1.1. Primary Analysis

The primary efficacy endpoint is the percent change from baseline in dystrophin levels (final concentration) following 40 weeks of ataluren therapy, as measured by ECL. The final concentration is calculated by dividing a sample's dystrophin concentration by its total protein concentration. In addition, the percentage of the predicted levels (% normal) will also be calculated as dystrophin levels normalized to dystrophin concentration of the control population ([Syneos Health Report No. 14597.051619.A](#)):

$$\% \text{ normal (in \%)} = 100 * \text{final concentration} / 33.8$$

Within each muscle location, the best, median, and the average of the dystrophin levels and the corresponding % normal values of the muscle cores will be summarized using descriptive statistics for each subject. In case any measured dystrophin concentrations are below the lower limit of quantification (LLOQ), the dystrophin concentrations will be set at 0.5\*LLOQ in the final concentration calculation for the statistical analysis.

The null hypothesis of the primary analysis is that the percent change from baseline in dystrophin levels following 40 weeks of ataluren therapy as measured by ECL is zero with the alternative hypothesis being that the change is greater than zero. To evaluate this hypothesis, a one-sided test at the 5% significance level will be employed.

The percent change from baseline at Week 40 in dystrophin levels measured by ECL will be analyzed using the mixed effect model repeated measurement (MMRM) analysis with factors of muscle locations, visits (baseline and Week 40) as fixed effects, and subjects as a random effect, based on ITT population. An unstructured covariance matrix will be used, and if the model fails to converge, then a compound symmetry matrix will be used. Since dystrophin level is known to be non-normally distributed, a log-transformation will be used in the analysis. The best dystrophin levels across all muscles are considered the primary analysis. A sample SAS code of the MMRM model is provided as follows:

```
proc mixed data = dataset;  
  
class subjid visit mlocation; /*mlocation is muscle location*/  
  
model lnaval = visit mlocation; /*lnaval is log-transformed dystrophin level*/  
  
random subjid;  
  
repeated visit / type = un;  
  
estimate "Week 40 change from baseline" visit -1 1;  
  
run;
```

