As supportive analyses, the average and median dystrophin levels across all muscles, and the subgroup analyses of the best, median, and mean dystrophin levels within each muscle location will be considered. In addition, the two-sided 90% confidence interval of percent change from baseline in dystrophin levels at Week 40 and the ratio (%) of dystrophin level at Week 40 versus baseline will also be provided.

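### The SAP sets two incompatible significance levels for the primary and secondary tests, one-sided 5% in the body and one-sided 0.025% in Section 10

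*SAP*

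**What the plan says.** Protocol 8.1 sets the original rule: "To evaluate this hypothesis a one-sided test at the 5% alpha level will be employed". SAP Section 10 lists changes to the protocol that it says are implemented in the SAP. The first is that "inference for the primary and secondary efficacy endpoints will be evaluated using a one-sided test at the 0.025% significance level", as requested by US FDA.

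The body of the same SAP reads otherwise:

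- Section 5.1, general rule: "Unless specified, all hypothesis testings are 1-sided at a 5% alpha level".
- Section 7.1.1, primary test: "a one-sided test at the 5% significance level will be employed". Section 7.2.1 applies the same method to the secondary endpoint.
- Section 5.5, gate: the secondary endpoint is analysed "if the primary efficacy endpoint is statistically significant at 0.05 significance level".
- Section 7.1.1, interval: "the two-sided 90% confidence interval of percent change from baseline in dystrophin levels at Week 40", with the Week 40 to baseline ratio reported as well.
- Section 3.3, Table 1: sample sizes for 85% power at one-sided 5%. For an increase of 0.08% and an intra-subject CV of 30%, "13 evaluable subjects would be required to have a power of 85% to detect this increase".

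**The concern.** Two live statements in one document give different thresholds for the only two formally tested endpoints. If the one-sided primary p-value falls between 0.025 and 0.05, Section 7.1.1 declares success and Section 5.5 opens the secondary test, while Section 10 says that the primary test has failed. The 90% interval could exclude no change in that same case. In an open-label, single-arm trial with one primary test, the success criterion has to be fixed before the result is known, and here it could be chosen afterwards.

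The printed figure adds a second problem. Taken literally, 0.025% is an alpha of 0.00025. The documents do not say that 0.025 was meant, although that is the likely reading. The only power statement in the SAP, 85%, was calculated at 5% and does not carry over to either reading of Section 10.

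**Working it through.** **Is Section 10 operative text?** Its other two changes are carried into the body. Section 7.1.1 runs the primary analysis on the ITT population without the baseline-level exclusion, and Sections 7.1.3 and 7.2.2 add the exclusion as a sensitivity analysis. Only the change of level is missing from the body. Section 10 therefore describes current intentions and is not a record of superseded text.

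**Inputs (SAP 3.3 and 7.1.1).** Baseline 0.2% of control; increases of 0.04, 0.06 and 0.08 percentage points; intra-subject CV of 20, 25, 30 and 35%; power 85%; one-sided alpha 5%; analysis on the log scale; planned enrolment 15 to 20.

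**Model.** The SAP gives no sample-size formula. I assumed a paired t-test on the log scale with exact noncentral-t power:

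- effect = ln(1 + increase/0.2), that is ln 1.2, ln 1.3 and ln 1.4
- SD of the within-subject difference = √2 × CV
- noncentrality = effect × √n / SD

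For the worked example, effect = ln 1.4 = 0.336, SD = √2 × 0.30 = 0.424, and at n = 13 noncentrality = 0.336 × √13 / 0.424 ≈ 2.86.

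**Reproducing Table 1 at one-sided 5%.** Eleven of the 12 cells match exactly. The other (0.06%, CV 35%) gives 27 against the published 28; power at 27 is 0.85004, so this is a matter of rounding. In the example, n = 13 gives 85.3% power.

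**Same model at the two readings of Section 10** (subjects for 85% power, CV 20/25/30/35%):

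| Increase | Published, 5% | One-sided 2.5% | One-sided 0.025% as printed |
|---|---|---|---|
| 0.04% | 19/29/41/55 | 24/36/51/69 | 56/83/117/157 |
| 0.06% | 10/15/21/28 | 13/19/26/34 | 30/44/60/79 |
| 0.08% | 7/10/13/18 | 9/12/17/22 | 21/29/39/51 |

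Cells reachable with 20 subjects: 7 of 12 at 5%, 5 of 12 at 2.5%, none at 0.025%.

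**Power at the published n, all 12 cells.** 74.3% to 77.6% at one-sided 2.5%; 5.3% to 18.4% at 0.025%.

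**Power for the worked example (0.08%, CV 30%), all subjects evaluable:**

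| n | 5% | 2.5% | 0.025% |
|---|---|---|---|
| 13 | 85.3% | 74.7% | 10.0% |
| 15 | 89.9% | 81.5% | 15.1% |
| 20 | 96.2% | 92.0% | 31.5% |

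**Sensitivity to the inferred SD.** With SD = √(2 ln(1 + CV²)) the example needs 16 subjects at 2.5% and 38 at 0.025%, and power at n = 13 and 2.5% is 76.5%. The conclusion is unchanged.

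**Matching interval.** A one-sided test at level α pairs with a two-sided interval of 100(1 − 2α)%: 90% for 5%, 95% for 2.5%, 99.95% for 0.025%. The SAP reports 90%.

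**The case against.** The strongest reply narrows the point without removing it.

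- **Table 1 names its own alpha and is arithmetically right for it.** That stands. The SAP nowhere claims 85% power at the Section 10 level; the table is out of date only if Section 10 governs.
- **The practical loss is moderate at 2.5%.** That also stands. The example needs 17, inside the planned 15 to 20, and power there is 81.5% to 92.0% if every subject is evaluable.
- **The 0.025% results rest on a probable slip.** Agreed. They show what the printed figure implies and should not be used to judge how serious the conflict is. The documents do not correct the slip, so it has to be corrected.
- **Section 5.1 is only a default, and the 0.05 in Section 5.5 has no sidedness.** Section 5.1 could give way to Section 10, and a two-sided 0.05 would equal one-sided 0.025. But the default in Section 5.1 is one-sided, and Section 7.1.1 specifies 5% for the primary test in its own words, so neither reading reconciles the document.
- **The 90% interval is supplementary and decides nothing.** True. The mismatch is one of presentation, but a reader will take an interval that excludes no change as agreeing with the test.
- **The planned analysis is a mixed model with muscle location, not a paired t-test.** True. The power figures are approximations under a model inferred from its match to Table 1.

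**Conclusion.** The point holds. The SAP contains two current and incompatible decision rules for the primary and secondary tests, and the outcome differs for any one-sided p-value between the Section 10 level and 0.05. This does not depend on how the printed figure is read or on any power model.

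If 2.5% is meant, 85% power becomes roughly 74% to 78% at the published sample sizes, the worked example moves from 13 to 17 subjects, and 5 of the 12 scenarios, down from 7, are reachable with 20. If 0.025% is meant as printed, none is reachable. These sizes assume a paired log-scale t-test with SD √2 × CV and no loss of evaluable subjects; the SAP states no dropout rate. Because the conflict bears on whether the trial is declared positive, it must be corrected before the results are analysed.

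**What to change.** - Confirm the level agreed with FDA and state it once, with its sidedness, in Sections 5.1, 5.5, 7.1.1 and 10. If it is 2.5%, write one-sided 0.025 (2.5%) and remove 0.025%.
- In Section 5.5, give the gate at that same one-sided level.
- Replace the 90% interval with the matching one: two-sided 95% if the level is 2.5%. A 90% interval may stay as an extra if labelled descriptive.
- Recompute Table 1 at the confirmed level and state the formula behind it. Alternatively, keep the table labelled as the planning calculation at 5% and add the power that 15 to 20 evaluable subjects give at the confirmed level (for 0.08% and CV 30% at 2.5%, 81.5% to 92.0%).

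The cost is SAP wording and one table. The stated power becomes less favourable. At 2.5% no additional patients are required for the worked example. If 0.025% really is intended, the SAP should say plainly that no scenario in Table 1 reaches 85% power with 20 subjects.
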